### **Specific Aims:**

**Aim 1.** Evaluate the efficacy of tamoxifen for treatment of low/intermediate-risk bladder tumors, assessing for the clinical response of the marker lesion, and analyzing the effects in tissue, in terms of affecting apoptosis and proliferation, while continuously monitoring for treatment toxicity.

**1a.** Evaluate the efficacy of tamoxifen for treatment of low/intermediate-risk bladder tumors, utilizing the RECIST criteria combined with the final biopsy of the marker lesion or the bed of the lesion in case of a complete response. (PRIMARY ENDPOINT)

**1b.** Evaluate the histopathologic effect of tamoxifen treatment in the tumor cells, assessing for the presence of necrosis, fibrosis, apoptosis and scar tissue.

**1c.** Evaluate the treatment effect in the histologic markers for apoptosis (TUNEL) and proliferation (Ki-67).

**1d.** Monitor treatment toxicity.

**Aim 2.** Evaluate the expression levels of ER $\alpha$  and ER $\beta$  (including splicing variants) before and after treatment with tamoxifen, in both normal and tumor tissues, and correlate the clinical response with the expression levels of these ERs.

**2a.** Report on and compare the pre and post-treatment expression levels of ER $\alpha$  and ER $\beta$  (including their splicing variants, more specifically ER $\beta$ -1, ER $\beta$ -2 and ER $\beta$ -5) in both normal and tumor tissues.

**2b.** Correlate the observed clinical effect, measured by the proportion of subjects that had complete or partial responses, with the pretreatment expression levels of ERs in tumor tissue.

**Primary objective:**

Evaluate the efficacy of tamoxifen for treatment of low/intermediate-risk bladder tumors, assessing for the clinical response of the marker lesion.

**Secondary objectives:**

While assessing for clinical response of the marker lesion, we will also analyze the effects in tissue, in terms of affecting apoptosis and proliferation, while continuously monitoring for treatment toxicity.

Additionally, we will evaluate the expression levels of ER $\alpha$  and ER $\beta$  (including splicing variants) before and after treatment with tamoxifen, in both normal and tumor tissues, and correlate the clinical response with the pretreatment expression levels of these ERs.

**Drug information:**

**A. Tamoxifen**

The manufacturer states that the adverse effect profile of tamoxifen in breast cancer patients generally appears to be similar for men and women. Adverse effects of tamoxifen citrate usually are relatively mild and rarely severe enough to necessitate discontinuation of the drug in patients with breast cancer. Tamoxifen usually is well tolerated in male patients with breast cancer. The main potential adverse effects reported in patients receiving tamoxifen are:

1. Cardiovascular effects, including thrombotic and venous thromboembolic events such as stroke, pulmonary embolism, and deep-vein thrombosis, fluid retention and edema.
2. Vasomotor symptoms (i.e. hot flushes).
3. Effects on lipoproteins (hyperlipidemias and hypertriglyceridemia).
5. Genitourinary and renal effects (vaginal discharge and menstrual irregularities, loss of libido and impotence, increased serum BUN and/or creatinine).
6. Musculoskeletal and bone pain, and hypercalcemia.
7. Ocular effects (retinopathy, corneal opacities, and decreased visual acuity).
8. Hepatic effects (increased serum AST (SGOT) or ALT (SGPT) concentrations, and increased bilirubin and/or alkaline phosphatase concentrations).

9. Gastrointestinal effects (nausea, anorexia, distaste for food, and abdominal cramps).
10. Nervous system effects (dizziness, lightheadedness, headache, fatigue, and mental depression).
11. Hematologic effects (thrombocytopenia and neutropenia, pancytopenia, and leucopenia).
12. Dermatologic effects (thinning and/or partial loss of hair).
13. Other Adverse effects (weight loss, fatigue, and cough).
14. Carcinogenicity (increased incidence of uterine cancer).
15. Pregnancy and fertility (tamoxifen may cause fetal harm when administered to pregnant women. Effects on reproductive function are expected from the anti-estrogenic properties of the drug).

**Phase of study:** Single-center, two-stage phase-II clinical trial (Simon design)

**Eligibility criteria:**

**Inclusion**

1. Males and females age 21 or older.
2. Histologic evidence of urothelial carcinoma of the bladder.
3. Low/Intermediate-risk papillary urothelial carcinoma of the bladder, at initial occurrence or recurrent with >6 months interval free of disease.
4. Patients with multifocal tumors must have resectable lesions.
5. Patients may be treatment-naïve or have failed previous regimen of intravesical therapy.
6. At least one endoscopically measurable tumor 6 - 10mm in diameter.
7. Adequate hepatic and renal function normal ranges defined as:  
Creatinine 0.6-1.3 MG/DL  
BUN 10-20 MG/dL  
AST (SGOT) 5-35 U/L  
ALT (SGPT) 7-56U/L  
GGT 0-45U/L
8. Patient or authorized proxy needs to have signed the informed consent form.

**General Exclusion**

1. Patients with sessile appearing tumors, which may be invasive or high-grade.
2. Diagnosis of urothelial carcinoma involving the prostatic urethra or upper urinary tract.
3. Plans for pelvic radiation while participating in the study.
4. Concurrent use of selective serotonin reuptake inhibitors or aromatase inhibitors.
5. Chronic or acute renal or hepatic disorder or any other condition, medical or psychological that, in the opinion of the investigator, could jeopardize the subject's safe participation.
6. Any other investigational drug within 30 days prior to registration and during the study.
7. Any subject who, in the opinion of the PI is at risk for thromboembolic events.
8. Any patients taking drugs that are known to have drug interactions with Tamoxifen will not be included.

**Women Exclusion**

1. Pregnant or lactating women.

2. Personal history of endometrial cancer or any abnormal uterine bleeding.
3. Previous or concurrent treatment with SERM and/or hormonal replacement therapy within 3 months of the study.

## **Design:**

### **Study design**

We will conduct a single-center, two-stage phase-II, clinical trial utilizing the marker lesion study design, where a tumor is mapped in the bladder, treated, and re-assessed after the study intervention to evaluate the effects of the therapy. This study design will allow the evaluation of the size of the tumor before and after treatment, and the histological assessment of treatment effect in normal and tumor tissues, as well as modulation of immunohistochemistry markers for apoptosis and proliferation, and of the expression levels of ER $\alpha$ , ER $\beta$ 1, ER $\beta$ 2, and ER $\beta$ 5.

### **Overall study description**

Patients with primary or recurrent low/intermediate-risk papillary urothelial carcinoma of the bladder will undergo resection of all but one marker lesion, measuring at least 6mm but no greater than 10mm, and biopsy of normal-appearing mucosa. Patients with a solitary tumor will undergo only biopsy prior to treatment. A 2mm cold cup biopsy of the marker lesion will always be performed to rule out a potential high-grade lesion and for assessment of pretreatment immunohistochemistry expression levels of ER $\alpha$ , ER $\beta$ 1, Ki-67 (proliferation marker) and TUNEL (apoptosis marker). If there are multiple tumors, all lesions, except the marker lesion will be resected and sent for analysis. These patients will not receive single immediate post-operative intravesical instillation of mitomycin-C. They will then undergo a 12-week course of treatment with tamoxifen administered as a single daily oral dose of 20mg. At the completion of therapy, patients will undergo resection of the marker lesion (or biopsy of the tumor bed, if a complete response is observed) and biopsy of normal-appearing bladder mucosa again. Toxicity evaluations will be performed at the beginning (day 3), midway (week 6), and at completion of treatment (week 12), prior to resection of the marker lesion. A final assessment for toxicity will also be performed 30 days after completion of therapy as well as a second definitive resection of the marker lesion. Urine samples will be obtained with the index tumor in place (marker lesion), and after completion of treatment, at the time of definitive transurethral resection of the index tumor, as part of the standard clinical care of these patients, and at the discretion of the surgeon for assessment of urinary cytology. The urine samples will not be utilized for the research study. All normal-appearing bladder biopsies (pre and post-treatment), the additional tumors (in case of multiple lesions), and the definitive resection of the marker lesion (in the absence of response to therapy) will provide sufficient material for immunohistochemistry assessment of the expression levels of ER $\alpha$ , ER $\beta$ -1, ER $\beta$ -2, ER $\beta$ -5, Ki-67, and TUNEL, and also for RT-qPCR for mRNA analyses of ER $\alpha$ , ER $\beta$ -1, ER $\beta$ -2, and ER $\beta$ -5. The pretreatment biopsy of the marker lesion will be performed with a smaller biopsy forceps and will provide limited material, sufficient only for immunohistochemistry assessment of the expression levels of ER $\alpha$ , ER $\beta$ -1, Ki-67, and TUNEL.

### **Marker lesion study design**

The marker lesion study design consists of deliberately leaving a small visible lesion in the bladder, so the patient can receive the study treatment, and shortly afterward have the lesion

removed and re-assessed for evaluation of treatment efficacy. Extensive natural history studies observing small low/intermediate-risk bladder tumors demonstrate that they grow slowly with very minimal risk of progression, and that they usually remain stable in size for at least 12 weeks without exhibiting spontaneous remission. The marker lesion should be papillary, since sessile tumors are likely high-grade, and should measure 6-10 mm in diameter. Patients with multiple tumors will have all visible disease resected with the exception of the marker lesion. A single small cold cup biopsy will be taken of the marker lesion, and a pilot study (H-33285) is being completed to prove that biopsying the marker lesion does not cause necrosis, fibrosis and scarring that can lead to confusion or mask either the primary or secondary endpoints. Because the natural history of this category of bladder lesions is so well-known and extensively described, there is no need for a control group in this study.

### **Collection of specimens**

A random biopsy of normal appearing mucosa remote from any tumor will be required pre and post-treatment. All immunohistochemistry studies will be performed on formalin-fixed paraffin-embedded tissue. Tissue destined to mRNA analysis will be directed to the research laboratory for analysis. . At the end of the trial, these specimens will be destroyed in an appropriate manner, according to the BCM rules and regulations.

### Office visit on 2nd Resection only occurs if patient had a single Tumor during 1st Resection. All patients with Multiple tumors at 1st Resection will have 2nd Resection in an outpatient hospital setting.

#### Completed per PI description

## **Procedures:**

**Aim 1 Procedures:** Transurethral resection of bladder tumors is a well-defined surgical technique used for diagnosis, staging, and treatment of bladder tumors of different stages. Briefly, patients undergo general anesthesia. Under proper aseptic technique, an optical resectoscope with video imaging capabilities is introduced into the bladder retrogradely via the urethra. The bladder tumor is resected using a resection loop connected to an electric source. The technique involves scooping movements of the loop, while cauterization is applied, to allow concomitant tissue cut and hemostasis. Measurement of the lesions will be performed by comparison with the standardized size of the resection loop.

Collection of samples: Biopsies of the marker lesion and normal appearing mucosa located remotely from the marker lesion will be processed using standard procedures for formalin fixation and paraffin embedding. These tissues will be tested by immunohistochemistry for Ki-67 and TUNEL. Each specimen will also be stained with hematoxylin and eosin to verify urothelial carcinoma histology.

**Aim 2 Procedures:** Collection of samples: Biopsies of the marker lesion and normal mucosa remote from the marker lesion will be processed using standard procedures for formalin fixation and paraffin embedding. The pretreatment biopsy of the marker lesion will be performed with a 2mm cold-cup biopsy forceps, to avoid affecting the histologic characteristics of the marker lesion. Because of the limited amount of tissue yield in this biopsy, we will only perform immunohistochemistry analyzing Ki-67, TUNEL, ER $\alpha$  and ER $\beta$ -1. The normal bladder biopsies, the resection of additional tumors synchronous to the marker lesion (in case of multiple lesions), and the final definitive resection of the marker lesion will be performed with a regular rigid biopsy forceps or resection loop, yielding much larger specimen fragments. These tissues will be tested by immunohistochemistry and RT-qPCR for the mRNA of ER $\alpha$ , ER $\beta$ -1, ER $\beta$ -2 and ER $\beta$ -5. Each specimen will also be stained with hematoxylin and eosin to verify urothelial carcinoma histology.

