### **Statistical considerations on the proposed analyses of the secondary aims, including the biomarker experiments**

**Specific Aim 1b:** We will assess the histologic aspect of both normal tissue and the bladder cancer marker lesion biopsies before and after treatment and compare for the presence of fibrosis, scarring, tumor necrosis and apoptosis. These data will be measured and quantified using light microscopy so percent positivity can be evaluated. Comparisons will be made between normal and tumor tissues (independent samples analysis), and also between pre and post-treatment on both normal and tumor tissues (paired samples analysis) to evaluate the effect with tamoxifen treatment. Non-parametric tests will be utilized as appropriate.

**Specific Aim 1c:** We will compare pre and post-treatment levels of immunohistochemistry staining levels of both the normal tissue and the marker lesion to detect changes in expression of TUNEL and Ki-67, associated with treatment (paired samples analysis). Nuclear immunoreactivity will be assessed by light microscopy and percent positive stained nuclei calculated. The percentiles will be analyzed as a continuous variable. Just like above, non-parametric tests will be utilized as appropriate.

The modulation of pre vs. post-treatment biomarker endpoints will be summarized and compared using the paired t-test or nonparametric paired tests as appropriate for quantitatively measured biomarkers, including Ki-67, and TUNEL. Independent analyses will likewise be employed to compare these biomarkers measured between normal mucosa and marker bladder tumor. We will

also assess the correlations of TUNEL and Ki-67 with rates of positive response. Descriptive statistics will be calculated to summarize these biomarkers at pretreatment, post-treatment, difference from pre to post-treatment, and percent change from pre to post-treatment. Histologic effect will also be considered as a secondary endpoint in determining response to therapy. Histologic effect in the lesion will be summarized descriptively using frequencies and proportions before and after treatment.

**Specific Aim 1d:** Toxicity data will be presented and summarized using descriptive statistics, tabulated using frequencies and percentages.

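### Aims 1b/1c compare a cold-cup marker-lesion sample before treatment with one that may be cut by a cauterising loop afterwards, so any instrument effect is confounded with tamoxifen

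*Combined protocol and SAP*

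**What the plan says.** Under Procedures (Aim 2), the pretreatment biopsy of the marker lesion is "performed with a 2mm cold-cup biopsy forceps, to avoid affecting the histologic characteristics of the marker lesion". For the end of treatment, the same paragraph says the "final definitive resection of the marker lesion will be performed with a regular rigid biopsy forceps or resection loop, yielding much larger specimen fragments". The choice between forceps and loop is left open. The Aim 1 paragraph of that section describes loop resection: "The technique involves scooping movements of the loop, while cauterization is applied, to allow concomitant tissue cut and hemostasis".

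The Overall study description says that at completion of therapy "patients will undergo resection of the marker lesion (or biopsy of the tumor bed, if a complete response is observed"). It also says that the definitive resection supplies tissue for Ki-67 and TUNEL, and that ERα and ERβ-1 immunohistochemistry is done on both the pretreatment biopsy and the final resection.

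The section on statistical considerations for the secondary aims uses these samples in two ways. Aim 1b will examine normal and tumour tissue before and after treatment and "compare for the presence of fibrosis, scarring, tumor necrosis and apoptosis", with paired tests meant to show the tamoxifen effect. Aim 1c will compare staining levels before and after treatment "to detect changes in expression of TUNEL and Ki-67, associated with treatment (paired samples analysis").

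The Marker lesion study design section states that no control group is needed. It mentions a pilot study of whether the first biopsy itself causes necrosis, fibrosis or scarring. I found no requirement to match instruments, leave cauterised areas out of scoring, record the instrument, or analyse by instrument.

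**The concern.** A paired before/after comparison in a single arm attributes to the drug everything that changes between the two samples. Here the sampling method can change together with the time point: cold 2 mm bite before, possibly a larger heat-cut specimen after. The plan gives protection of the lesion's histology as the reason for the small cold-cup forceps at the first biopsy, but says nothing comparable about the second specimen.

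At stake is the mechanistic evidence. Hypothesis 1 holds that tamoxifen acts by inducing apoptosis, and Aims 1b and 1c are where the trial looks for that. If the instrument shifts the readings, a significant change in TUNEL, Ki-67 or necrosis may not be a drug effect, and a true drug effect may be hidden.

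**Working it through.** **1. Is the mismatch in the text?** For the marker lesion:

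| | Before treatment | After treatment |
|---|---|---|
| Instrument | 2 mm cold-cup forceps, always | Rigid forceps or resection loop, not fixed |
| Cautery | No | Yes if the loop is used |
| Specimen | Limited material | Much larger fragments |
| Used for | Necrosis, apoptosis, TUNEL, Ki-67, ERα, ERβ-1 | The same readouts |

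**2. Does anything in the plan separate instrument from drug?**
- Control group: none. The stated reason is the well-known natural history of these lesions, including stable size. That does not speak to staining in a specimen cut another way.
- Pilot study: it concerns injury from the first biopsy, not how the second specimen is cut.
- Normal mucosa: forceps or loop is allowed at both times, so it does not undergo the lesion's cold-cup-to-loop change.

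**3. Reproduce the plan's own power figures.** Inputs for TUNEL, from the TUNEL power section: baseline mean 17, difference 5.1, SD of differences 5.13, n = 17, two-sided 5% paired t-test. The noncentrality is ncp = (difference / SD) × √n, referred to a noncentral t with n − 1 = 16 degrees of freedom and critical value 2.120.
- Difference 5.1: ncp = (5.1 / 5.13) × √17 = 4.099; power 97.0% (plan: 96.7%; a shifted central t gives 96.7%).
- Difference 3.71: ncp = (3.71 / 5.13) × √17 = 2.982; power 79.9% (plan: 80%).
- Ki-67, from its own power section: ncp = (1.101 / 1.41) × √17 = 3.220; power 85.6% (plan: 85.6%).

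The calculation has no term for a difference between instruments.

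**4. Illustrate a shift when the drug does nothing.** Put an assumed mean instrument shift in place of the drug effect. The shift sizes are assumptions.

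| Readout (n = 17) | Assumed mean shift | ncp | Probability of rejection |
|---|---|---|---|
| TUNEL | 0 | 0 | 5% |
| TUNEL | 1 point | (1 / 5.13) × √17 = 0.804 | 11.8% |
| TUNEL | 2 points | (2 / 5.13) × √17 = 1.607 | 32.7% |
| Ki-67 | 10% of 3.67 = 0.367 | (0.367 / 1.41) × √17 = 1.073 | 17% |
| Ki-67 | 20% of 3.67 = 0.734 | (0.734 / 1.41) × √17 = 2.146 | 52% |

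These shifts are averages over all 17 pairs. If only a fraction f of pairs is cut by loop and each of those shifts by s, the average is f × s. For example, 2 points in half the pairs gives 1 point.

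**5. Illustrate the opposite direction.** If a shift of 10% of baseline (1.7 points) opposes a true TUNEL change of 5.1, the net difference is 5.1 − 1.7 = 3.4, and power at n = 17 falls from 97% to 73%.

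**The case against.** The strongest reply is that nothing in the documents shows that the artefact exists at a size that matters. No section says what cautery does to TUNEL, Ki-67 or necrosis. The final fragments are much larger than the first bite, so any heat damage at a cut edge may touch little of the scored area. The plan permits forceps, in which case there is no cautery. Complete responders have a bed biopsy. Each of these dilutes an average shift. All of this stands, and it is why the figures above are illustrations and not estimates.

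Three stronger readings are tempting and are not supported:

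- **That the artefact favours the trial's hypothesis.** A reader might infer that heat raises TUNEL and necrosis and lowers Ki-67. The documents give no direction, and an opposing artefact would cost power instead. Nor does the 80% rejection rate at a shift of 3.71 points measure the artefact: 3.71 is the plan's own detectable difference at 80% power, so any shift of that size gives 80%.
- **That the planned correlation of TUNEL and Ki-67 with response is contaminated.** The plan does not say which time point is correlated, and pretreatment values all come from cold-cup samples. The final procedure separates complete responders from everyone else, but partial responders, who count as successes, are resected just as patients with stable or progressive disease are.
- **That Aims 1b/1c cannot inform the mechanism at all.** Pairs in which no loop was used carry no cautery difference.

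What the reply does not remove is that the plan neither fixes nor records which pairs those are, and has no rule for scoring cauterised fields.

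**Conclusion.** The point holds for secondary Aims 1b and 1c: instrument and time point are confounded wherever the post-treatment sample is cut by loop, and the analysis plan assigns the whole paired change to tamoxifen. The size and direction of any instrument effect are unknown from the documents. If it averaged 1 or 2 TUNEL points, the nominal 5% test would reject for an inactive drug in about 12% or 33% of trials. These figures assume the plan's SD of 5.13, 17 complete pairs and an approximately normal difference. That SD derives from repeat tissue-microarray cores, so it is not shown to include variation between instruments.

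The primary composite response endpoint and the Simon decision rule are not touched. This is worth correcting because the remedy is cheap and the instrument is best recorded as specimens are taken, but it does not threaten the trial's main conclusion.

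**What to change.** Add to the statistical considerations for Aims 1b and 1c:

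1. Necrosis, apoptosis, TUNEL and Ki-67 are scored only in fields free of cautery artefact, at both time points. The same rule applies to the pre/post ERα and ERβ-1 immunohistochemistry on the same specimens.
2. The instrument is recorded for every specimen.
3. The paired results are reported for all pairs and, separately, for pairs without loop sampling.

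This needs protocol wording, one data field and an instruction to the pathologist. It needs no extra visit, procedure or reader. The cost is a smaller scored area and possibly some unscorable loop specimens, so the number of scorable pairs should be reported. With 14 pairs, the plan's inputs give power of 77% for Ki-67 and 93% for TUNEL. The rule does not remove the difference in specimen size. Scoring percent positivity limits that problem, but a larger specimen can still show focal necrosis or fibrosis that a 2 mm bite misses, and the report should say so.

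Using the forceps that the Procedures section already permits for the paired-readout tissue is optional. That section does not describe the final forceps as cold, so the wording would have to be made explicit. A separate fragment is also an added sampling step that divides a small specimen. If it is done, the plan must state that all fragments count toward the final biopsy result in the End-points section.
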